## **AE Attribution Scale**

Relationship of event to study procedures:

**None** – the event can be readily explained by some other cause or no relationship exists between the study procedures and the event.

**Unlikely** – the temporal relationship between the event and the administration of the study procedures is uncertain and it is likely that the event can be explained by other causes.

**Possible** – there is some logical temporal relationship between the event and the administration of the study procedures and the event is unlikely to be explained by other causes. This category may include incidents that arise from use or attempted use of a strategy prescribed in a case management session.

**Probable** – the temporal relationship is compelling between the administration of the study procedures and the event cannot be explained by other causes. This category may include incidents that arise from use or attempted use of a strategy prescribed in a case management session.

## **AE Documentation**

Each incident that meets the definition of an AE as listed above will be documented via entry into the appropriate data form on the NDSC website within a month of when the incident was detected by research staff. NDSC staff will send a reminder email to study coordinators to enter data for AEs within the past month.

## **SAE Reporting and Documentation**

SAEs that are unanticipated and possibly related to the study intervention will be reported to the respective site PI, the lead site PI, chair of the DSMB, the respective IRB, and the PCORI Program Official in accordance with requirements.

1. Unanticipated fatal or life-threatening SAEs related to study procedures will be reported to all parties listed above immediately.
2. Other unanticipated SAEs related to study procedures will be reported to the respective site PI and lead site PI within 24 hours. The SAE will be reported to the respective IRB according to that institution's requirements. The event will be reported to PCORI promptly but no later than 10 days after reporting the event to the IRB.
3. Anticipated or unrelated SAEs will be reported to the DSMB and PCORI as part of the bi-annual and annual DSM reports. These DSM reports will also be submitted to each site's IRB.

Study researchers will contact the Chair of the DSMB when an SAE that fits into the first two categories listed above is discovered within one week of discovery. The Chair of the DSMB will use his discretion to determine whether the other DSMB members should also provide additional consultation. The chair will then provide any suggestions for corrective action within two weeks of notification.

Each incident that fits into the first two categories listed above will be documented via entry into the appropriate data form on the NDSC website within 5 business days of when the incident was detected by research staff. Each incident that fits into the third category listed above will be documented via entry into the appropriate data form on the NDSC website within one month of when the incident was detected by research staff.

As per PCORI guidelines, any decision, finding, recommendation or action of the DSMB or IRB relating to any SAEs will be reported to PCORI promptly but no later than 10 days after the decision, finding, recommendation or action has been made.

### **Unanticipated Problems Information: Definition**

Study researchers consider *unanticipated problems*, in general, to include any incident, experience, or outcome that meets **all** of the following criteria:

- unexpected (in terms of nature, severity, or frequency) given (a) the research procedures that are described in the protocol-related documents, such as the IRB-approved research protocol and informed consent document; and (b) the characteristics of the participant population being studied;
- at least possibly related to participation in the research (in this guidance document, *possibly related* means there is a reasonable possibility that the incident, experience, or outcome may have been caused by the procedures involved in the research); and
- suggests that the research places participants or others at a greater risk of harm (including physical, psychological, economic, or social harm) than was previously known or recognized.\*
- An adverse event is an unanticipated problem if it meets the three criteria described above.

For the purposes of this study, breach of confidentiality or inappropriate access to protected health information are considered serious unanticipated problems and will be shared with the DSMB.

\* Source: <https://www.hhs.gov/ohrp/regulations-and-policy/guidance/reviewing-unanticipated-problems/index.html#Q2>

### **Unanticipated Problems: Documentation and Reporting**

Any event that is unanticipated, places subjects or others at a greater risk of harm (including physical, psychological, economic, or social harm) than was previously known or recognized, and possibly related to the study procedures will be reported to the respective site PI, the lead site PI, chair of the DSMB, the respective IRB, and the PCORI Program Official in accordance with requirements.

1. Breaches of confidentiality or inappropriate access to protected health information will be reported to all parties listed above immediately.
2. Other serious unanticipated problems related to study procedures will be reported to the respective site PI and lead site PI, within 24 hours. The unanticipated problem will be reported to the respective IRB according to that institution's requirements. The event will be reported to PCORI promptly but no later than 10 days after reporting the event to the IRB.

Study researchers will contact the Chair of the DSMB when an unanticipated problem is discovered within one week of discovery. The Chair of the DSMB will use his discretion to determine whether the other DSMB members should also provide additional consultation. The chair will then provide any suggestions for corrective action within two weeks of notification.

Each incident that meets the definition of an unanticipated problem will be entered into the appropriate data form on the NDSC website within 5 business days of when the incident was detected by research staff.

As per PCORI guidelines, any decision, finding, recommendation or action of the DSMB or IRB relating to any SAEs will be reported to PCORI promptly but no later than 10 days after the decision, finding, recommendation or action has been made.

### **Protocol Deviations, Violations, Other Pertinent Documentation**

Study researchers will document any protocol deviations, violations or events that may jeopardize the integrity of the study in a 'Note-to-File' using a standardized template across all sites. Regarding protocol deviations: staff will document only deviations that are within the control of research staff, for example completing a questionnaire outside of the questionnaire window. Research staff will not document deviations outside of the staff's control, however, for example when a patient fails to be available for a study questionnaire. Each incident will be entered into the appropriate data form on the NDSC website within a month of when the incident was detected by research staff. NDSC staff will send a reminder email to study coordinators to enter data for any pertinent incidents within the past month.

### **Data Safety Monitoring Board (DSMB)**

A Data Safety and Monitoring Board (DSMB) will be led by [name], PI of the University of Alabama Birmingham TBIMS, [name] a biostatistician from Montana State University and a currently unidentified TBI patient and family member. The DSMB will monitor the study and review the following: a) participant recruitment, accrual, retention, and withdrawal information; b) adverse events (AEs) and serious adverse events (SAEs); c) comparison of events that occur between treatment arms; d) individual events of particular concern; e) participant interview and/or performance status outcomes; f) other safety-supporting data requested by the DSMB; and g) summary of protocol violations, completeness and timeliness of study visit data, enrollment eligibility and ineligibility information, noncompliance, and unanticipated problems. Safety monitoring will focus on detection and monitoring of adverse events at the individual participant level.

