**Facility**

- nursing home (includes med-center, residential, institutions licensed as hospitals but providing essentially long-term, custodial, chronic disease care, etc.)
- subacute care (includes subacute hospital bed, skilled nursing facility)

The actual act of randomization will be automated via the NDSC BRITE website. Specifically, research staff will click the 'Randomize' button located in the 'Keys' tab of the 'Patient Post-Discharge Information' section under the 'Data' tab once the discharge destination has been entered. The randomization assignment will be automatically recorded in the BRITE website database.

These randomization procedures have been used by our team in prior studies where telephone follow-up was randomly assigned following discharge.

Once randomization occurs, their random assignment will be communicated to the TBI Care Manager (TCM). The TCM will then send out a letter to the patient participant and caregiver (if applicable).

For those who are randomized to the RDP arm, the letter will state that they will be contacted for follow-up at 3, 6, 9 and 12 months post hospital discharge and one year following injury (if applicable).

For those who are randomized to the RTP arm, in addition to a reminder of the follow-up data points as above, the letter will include a reminder of the specific goals of the study and the plan for follow-up calls with the TCM.

The meeting schedule will be modified throughout the intervention time period to fit the needs of both the patient and caregiver participants and may include evening or weekend appointments.

The TCM will also send patient and caregiver participants assigned to the RTP group a brief description of the general role of the TCM as well as a description of the specific TCMs at each site including education and work experience. This form may be mailed with the randomization letter, or part of a subsequent mailing.

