##### *Scheduling of Contacts*

Participants randomized to the RTP comparator at the point of hospital discharge will receive about 12 scheduled contacts over the next 6 months from a TCM. The TCM will be a contract employee hired specifically for this study. The TCM will be responsible for managing both the

logistics and content of the treatment with the support of a team of experienced TBI clinicians. Training of the TCM will be a key aspect of this study. The TCM will be either an MSW or have comparable experience in health care and/or social services but will not necessarily be experts in the field of TBI. The contacts will at minimum be by telephone; although many of our patient and family partners were also enthusiastic about the idea of using a HIPAA-compliant screen-to-screen feature (e.g., Zoom®) based on individual preference. Contacts may be in person if convenient for both participant(s) and TCM, e.g. the patient has a medical appointment near the TCM's office. A typical schedule of contacts that was vetted through our Patient and Family Stakeholders will be as follows: weekly, starting 1 week after discharge, for 4 weeks; biweekly for 2-3 months, depending on individual progress and needs; then monthly for 2-3 months.

The duration of each contact will depend on the needs of the patient/caregiver. For example, if the patient is not reporting unmet needs on the needs assessment, the contact may be very brief. However, it was the emphatic recommendation of the Patient and Family Stakeholders that all 12 scheduled contacts take place. As one stakeholder put it, *'If you're under water, you don't know if it's raining!'*

Additional Interim contacts may also take place during RTP, e.g., for TCM follow-ups or urgent questions, respectively, depending on the needs of the patient/caregiver (see below for more details).

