#### *Content of Scheduled Contacts*

The *content* of these contacts may include:

- (1) **Review of Discharge Plan:** Particularly in the first few calls, review of discharge plans and assistance and/or directive problem-solving around any obstacles to following discharge plans;

	Discharge from Inpatient Rehabilitation	Post-Discharge
Standardized Discharge Care	Patient and Family Education on diagnosis/needs	Phone call within a few days of discharge to reinforce discharge plan
	Written Discharge Instructions	
	Organize outpatient service/appointments	
	Medication teaching and prescriptions	
	Discharge summary sent to Primary Care Physician	
Optimized Transition Care	Patient and Family Education	Phone call within a few days of discharge
	Written Discharge Instructions	Ongoing telephone contacts until 6-months post-discharge
	Organize outpatient service/appointments	Review discharge plan and provide assistance to ensure follow through
	Medication teaching and prescriptions	Assess unmet needs
	Discharge summary sent to Primary Care Physician	Connect with relevant resources in healthcare network, community, etc.
		Assist with scheduling appointments/arranging transportation
		Provide reminder calls
		Follow up letter/email
		TBI Helpline to receive questions/request

(2) **Assessment of unmet needs:** Assessment of unmet needs, which has been standardized into a checklist of areas of need that are relevant to TBI, culled from literature on need fulfillment in this population, will take place at each scheduled contact. As one stakeholder with TBI stated: *"One thing I'm concerned about is if the care manager just asks basic questions to people such as "are things going well?" You will actually miss out on a lot of important detail about people's lives problems and the issue they are having."* (Patient Stakeholder) This checklist assesses specific needs for help with practical issues such as medication management and coordinating rehabilitation services; managing problematic symptoms such as pain, or addressing substance use; emotional issues such as managing daily stress and

controlling temper; psychosocial issues such as re-engaging with friends and leisure activities; caregiver issues such as role changes and caregiver stress; and participation-related issues such as finding employment.

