### **Masking (or Blinding)**

This study uses **masked outcome assessment**, which means that staff members who collect outcomes data from both patient and caregiver participants at 3-, 6-, 9- and 12 months must be unaware of patient participants' treatment group allocation. Several procedures are used to help outcomes staff to remain unaware of group assignment.

Randomization will be automated via a NDSC database to minimize unblinding. Specifically, research staff or the TCM will enter discharge destination and study site into the specified NDSC database as part of the discharge destination and date form. Subsequently the TCM will be notified via email of group assignment. Ideally, group assignment will be known only by coordinators and the TCM(s) at a given site, and the data coordinator at Craig Hospital.

In addition, only TCMs will have access to the 'Notes' tab on the NDSC database where adverse events, serious adverse events (SAE), unanticipated problems and note-to-files are entered. The reason is that blinded assessors would be unblinded if they observed entries for these events if entered by a TCM. As a result, all information relating to adverse events, SAEs, unanticipated problems and note-to-files will be sent by blinded assessors to the TCMs at each site for entry into the database.

Other procedures for preventing inadvertent unmasking will be used such as ensuring that data collectors and TCMs are not using office spaces in close proximity while TCMs are contacting patient participants, and minimizing the meetings that data collectors and TCMs attend in

common. Also, data collectors will not have access to the treatment list serve to prevent inadvertent unmasking from that source.

Staff will continue with a post-discharge questionnaire even if unblinded during the questionnaire administration, but will attempt to have another staff member (if available) administer subsequent questionnaires.

We will record on each post-discharge questionnaire any potential unblinding incidents by asking assessors: 1. if they believe they were unblinded during the questionnaire or any previous questionnaire; and 2. to guess which study arm they believe the participant was assigned to.

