**Study Discontinuation**

[figure not shown]
Participation in the study will be stopped prior to its completion if: (1) the RTP approach is associated with adverse effects that call into question the safety of this approach; (2) any new information becomes available during the trial that necessitates stopping the trial; or (3) other situations occur that might warrant stopping the trial.

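### Adverse events are compared between arms with no allowance for RTP's extra care-manager contacts, so at equal true rates RTP is expected to show more recorded events

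*Combined protocol and SAP*

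**What the plan says.** The Data Safety Monitoring Board (DSMB) section lists a "comparison of events that occur between treatment arms" among the items reviewed. It gives no method, no time points and no rule on how the events must have been found. Under Annual DSM Report and Meeting, the yearly report takes up whether the trial should go on in light of adverse events to date. Study Discontinuation names as one ground for stopping that "the RTP approach is associated with adverse effects that call into question the safety of this approach".

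Under AE Documentation, an event is entered once staff have learnt of it. The adverse event definition asks for a new or clearly worsened condition that led to, or called for, treatment by a clinician. No schedule for eliciting adverse events is given.

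The Randomization/Post-Discharge Transition Phase section sets out what RDP participants can expect: "the letter will state that they will be contacted for follow-up at 3, 6, 9 and 12 months post hospital discharge". RTP participants have the same questionnaires. In addition they "will receive about 12 scheduled contacts over the next 6 months from a TCM", typically "weekly, starting 1 week after discharge, for 4 weeks; biweekly for 2-3 months, depending on individual progress and needs; then monthly for 2-3 months". An unmet-needs checklist that covers symptoms such as pain "will take place at each scheduled contact", and "Additional Interim contacts may also take place during RTP". Other Components of RTP adds a care-manager telephone, e-mail and text route for RTP families.

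Masking (or Blinding) explains that "blinded assessors would be unblinded if they observed entries for these events if entered by a TCM". For that reason assessors pass the events they find to the care managers, who enter everything.

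**The concern.** A comparison of event counts is like-for-like only if an event has the same chance of being recorded in either arm. Here one arm has a detection route that the other lacks. The treatment-based threshold adds to this: care managers identify needs and help arrange care, so the intervention can itself move a complaint over the line into a recorded event.

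The route cannot be recovered from who made the entry, because care managers enter the events of both arms. No section limits the comparison to common time points, asks for the detection source in the tables, or tells the DSMB to allow for unequal detection.

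The DSMB could therefore see an excess in RTP that is only better detection, or a real reduction under RTP could be hidden. The same applies to any arm-level event table in the trial's reports.

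**Working it through.** **1. The plan's own figure: about 12 contacts.** The typical schedule gives 4 weekly contacts, then 2 per month for 2-3 months (4 to 6), then 1 per month for 2-3 months (2 to 3).
- All combinations: 4 + 4 + 2 = 10 up to 4 + 6 + 3 = 13.
- Combinations that fill exactly 6 months: 4 + 4 + 3 = 11, or 4 + 6 + 2 = 12.

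So the stated figure reproduces.

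**2. Scheduled study contacts by arm.**
- By month 6: RDP 2 questionnaires; RTP 2 + 12 = 14.
- By month 12: RDP 4; RTP 4 + 12 = 16.

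Interim contacts are not counted, and neither is the one-year-after-injury interview, which does not depend on arm. These are contacts at which staff may learn of an event. They are not occasions on which adverse events are formally asked about.

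**3. Expected ratio with equal true rates.** The documents give no detection rates, so three quantities are assumed:
- q: share of events captured through the questionnaires, the same in both arms;
- t: share of the events so missed that a care manager picks up while RTP contacts run (0.25 to 0.8);
- f = 0.5: share of events that fall in months 0-6.

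RDP detection is q. RTP detection is q + (1 - q) × t × f over 12 months, and q + (1 - q) × t in months 0-6. Example at q = 0.7, t = 0.5: (0.7 + 0.3 × 0.5 × 0.5) / 0.7 = 0.775 / 0.7 = 1.107.

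| q | 12 months, t = 0.25 / 0.5 / 0.8 | Months 0-6, t = 0.25 / 0.5 / 0.8 |
|---|---|---|
| 0.5 | 1.125 / 1.25 / 1.40 | 1.25 / 1.50 / 1.80 |
| 0.7 | 1.054 / 1.107 / 1.171 | 1.107 / 1.214 / 1.343 |
| 0.9 | 1.014 / 1.028 / 1.044 | 1.028 / 1.056 / 1.089 |
| 1.0 | 1.00 throughout | 1.00 throughout |

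The ratio is never below 1 and equals 1 only if the questionnaires miss nothing. The protocol's own target for questionnaire completion is 80%, so full capture cannot be presumed. If events cluster early after discharge, f exceeds 0.5 and the 12-month figures move towards the 0-6 month column.

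**4. How often this would look like a signal.** This is an illustration only, since the plan specifies no adverse-event test. It uses 450 per arm followed for 12 months, Poisson counts, and a Wald test of the log rate ratio at two-sided 0.05. The event rates are the two that the power section quotes for other purposes (0.42 and 2.25 per year), with 1 per year assumed between them.
- q = 0.7, t = 0.5, rate 0.42: expected events 450 × 0.42 × 0.7 = 132 against 450 × 0.42 × 0.775 = 146. The standard error is √(1/132 + 1/146) = 0.120 and ln(1.107) = 0.102, so z = 0.85 and the chance of p < 0.05 is about 14%.
- Same q and t: 26% at 1 per year and 50% at 2.25 per year.
- q = 0.9, t = 0.5: 6% to 9% across the three rates.
- q = 0.9 over the whole range of t and rates: the RTP count exceeds the RDP count in 55% to 83% of trials, against 50% with no bias.

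**5. After the change.** Restricted to questionnaire-found events there are 4 scheduled occasions per arm and the expected ratio is q / q = 1.00. This holds provided RTP participants repeat to the assessor what they have told the care manager.

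**The case against.** The strongest case against has five parts.

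- **No mechanical link to stopping.** Study Discontinuation sets no boundary and does not cite the arm comparison. The DSMB section says monitoring centres on single participants, each event is rated for its relationship to study procedures, and the board may ask for further unblinded analyses. This stands. A reader might infer that the biased comparison would itself trigger a stop; the documents do not say so. They do keep the comparison in the remit and let observed events bear on continuation.
- **Contacts are not solicitations.** A reader might infer that patients are asked about adverse events 14 times against 2. The listed questionnaire measures hold no adverse-event item, and care-manager calls are needs assessments that may be short. This stands, but because recording depends on staff awareness, more contact still means more opportunity.
- **Serious events are largely covered.** Hospitalisations and emergency visits come from the Cornell Services Index in both arms, through masked assessors, and are already analysed under Aim 3. This stands and confines the problem mainly to non-serious events in months 0-6.
- **The form cannot be inspected.** The problems report form and the separate monitoring plan are not in the file, so a source field may already exist. In that case only the tables need to change.
- **Restricting the whole comparison to questionnaire-found events would do harm.** It could lose deaths, events in patients who miss questionnaires, and harms specific to RTP. The AE Attribution Scale itself names incidents arising from a strategy given in a case-management session. This stands, and the fix below avoids it.

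**Conclusion.** The point holds as an expected bias against RTP in the all-source event comparison. Its direction follows from the design if true rates are equal and questionnaire capture is the same in both arms. Its size does not follow from the documents: the 12-month ratio of about 1.40 down to 1.01 rests on assumed capture of 50% to 90%, assumed care-manager pick-up of 25% to 80%, and half of events falling in months 0-6.

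Two stronger readings are not supported. RTP will not necessarily look less safe in this trial: at 90% capture the 12-month excess is at most about 4%. And the 1.80 at the top of the months 0-6 column is one corner of an assumed grid, not an estimate for the trial, whose DSM reports are cumulative and whose follow-up runs 12 months.

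Version 15.0 is dated January 2023, after the 10/31/2022 milestone for 12-month follow-up, so early stopping is largely moot. The point still bears on the final DSMB report and on the results reporting that follows. It does not touch the primary outcome analysis.

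**What to change.** Record how each event was first detected: care-manager contact, scheduled questionnaire, or other. Where the field was not collected, code it retrospectively from the care-manager contact records as far as they allow. Then:

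- tabulate all adverse and serious adverse events by arm and by source;
- for non-serious events, take the contrast restricted to the 3-, 6-, 9- and 12-month questionnaires as the like-for-like comparison, with the all-source table beside it;
- compare hospitalisations and emergency visits using the Cornell Services Index;
- keep all deaths, serious events and events possibly related to study procedures in the arm comparison whatever their source.

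Review of individual events is unchanged. The cost is one form field or some retrospective coding, extra columns in the DSMB tables, and fewer events in the common-source contrast. That contrast may also under-count events that RTP participants have already told the care manager and do not repeat, which would lean towards RTP; this is why the all-source table stays alongside.
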